Appendix F: MDS/MPN RESPONSE CRITERIA

(Cheson, *et al.*, 2006)

F.1 Antitumor Effect – Myelodysplastic Syndrome / Myeloproliferative Neoplasm

F.1.1. Complete Remission (CR)

Requires that all of the following be present:

Peripheral Blood Counts:

- Hemoglobin greater than 11 g/dL (untransfused, 4 weeks since last transfusion, subject not on erythropoietin).
- Neutrophils 1,000/mm³ or more (not on a myeloid growth factor)
- Platelets 100,000/mm³ or more (not on a thrombopoietic agent)
- Blasts, 0%
- No dysplasia

Bone Marrow Aspirate and Biopsy:

- Less than 5% myeloblasts
- Normal maturation of all cell lines
- No evidence for dysplasia

When erythroid precursors constitute less than 50% of bone marrow nucleated cells, the percentage of blasts is based on all nucleated cells; when there are 50% or more erythroid cells, the percentage blasts should be based on the nonerythroid cells.

F.1.2 Partial Remission (PR):

Requires that all of the criteria for complete remission be satisfied except blasts decreased by 50% or more over pretreatment. Cellularity and morphology are not relevant. Persisting dysplasia is permitted.

Hematologic Improvement (HI)-major (must have at least one of the three listed below)

must

persist for a minimum of 8 weeks to be considered a confirmed response.

- HI-major Erythroid: For subjects with pretreatment hemoglobin less than 11 g/dL, greater than 2 g/dL increase in hemoglobin; for RBC transfusion-dependent subjects transfusion independence.
- HI-major Platelet: For subjects with a pretreatment platelet count less than 100,000/mm³, an absolute increase of 30,000/mm³ or more; for platelet transfusion dependent subjects, stabilization of platelet counts and platelet transfusion independence.
- HI-major Neutrophil: For absolute neutrophil count (ANC) less than 1000/mm³ before therapy, at least a 100% increase, or an absolute increase of more than 500/mm³, whichever is greater.
- HI-major Trilineage: Trilineage response will require the demonstration of HI-major for each of the blood lineages (erythroid, platelet, neutrophil). Trilineage hematologic improvement will also apply to subjects who achieve adequate counts in all three lineages even if one or more lineages was adequate prior to treatment. Thus, all subjects who normalize all three lineages (within IWG definitions) for 8 weeks, but who do not meet the criteria for PR, will be considered HITrilineage.

F.1.3 Cytogenetic Responses

CONFIDENTIAL

This document is confidential. Do not disclose or use except as authorized.

- Complete cytogenetic response: An abnormal clone is detected in all metaphases prior to treatment and only normal metaphases are observed in all metaphases following treatment. Partial cytogenetic response: An abnormal clone is detected in all metaphases prior to treatment and the post-treatment sample has 50% or fewer abnormal metaphases compared to the pretreatment value.
- Cytogenetic non-response: An abnormal clone is detected in all metaphases prior to treatment and neither complete nor partial cytogenetic response is observed in posttreatment specimens
- Specimens with normal cytogenetic results before treatment will not be evaluated for cytogenetic response. The method used to determine cytogenetic response will be standard metaphase cytogenetics.

F.1.4 Progressive Disease

At least one of the following four criteria must be met:

1. An increase of $\geq 50\%$ in blasts relative to baseline, to at least the level shown below for different baseline levels:
2. Baseline blasts must increase to
 - $< 5\% > 5\%$
 - ≥ 5 and $< 10\% > 10\%$
 - ≥ 10 and $< 20\% > 20\%$
 - $\geq 50\%$ reduction from maximum remission/response levels in granulocytes or platelets.
 - Reduction in Hb concentration by at least 2g/dL or development of transfusion dependence.

F.1.5 Relapse

Relapse after CR or PR: one or more of the following:

- Return to pretreatment bone marrow blast percentage,
- Decrement of 50% or greater from maximum remission/response levels in granulocytes or platelets,
- Reduction in hemoglobin concentration by at least 2 g/dL or transfusion dependence.
- Progression after Hematologic Improvement: One or more of the following:
 - Decrement of 50% or greater decrement from maximum response levels in granulocytes or platelets,
 - A reduction in hemoglobin concentration by at least 2 g/dL or transfusion dependence.

F.1.6 Persistent Disease

[figure not shown]
- Hematologic Persistence – Cytopenias not attributable to other post-transplant causes accompanied by characteristic morphological changes $> d +90$ following alloSCT.
- Cytogenetic Persistence – Persistence of clonal abnormality $> d +90$ following alloSCT

CONFIDENTIAL

This document is confidential. Do not disclose or use except as authorized.

Appendix G: MANAGEMENT OF IMMUNE RELATED AEs DUE TO IPILIMUMAB

[figure not shown]
GI TOXICITY, HEPATOTOXICITY, ENDOCRINOPATHY, NEUROPATHY AND SKIN TOXICITY MANAGEMENT

CONFIDENTIAL

This document is confidential. Do not disclose or use except as authorized.

GI Toxicity Management Algorithm

*G4 = life-threatening, perforation

[figure not shown]
*Some patients have required a second dose of infliximab

Patients on IV steroids may be switched to oral corticosteroid (e.g., prednisone) at an equivalent dose at start of tapering or earlier, once sustained clinical improvement is observed. Lower bioavailability of oral corticosteroids should be taken into account when switching to the equivalent dose of PO corticosteroids.

CONFIDENTIAL

This document is confidential. Do not disclose or use except as authorized.

Hepatotoxicity Management Algorithm

*Ipilimumab may be held/delayed rather than discontinued if AST/ALT $\leq 8 \times$ ULN and Tbili $\leq 5 \times$ ULN. Resume ipilimumab when AST/ALT/Tbili return to grade 2 and meet protocol specific retreatment criteria.

**The recommended starting dose for grade 4 hepatitis is 2 mg/kg/day methylprednisolone IV.

[figure not shown]
*** MMF, mycophenolate mofetil

Patients on IV steroids may be switched to oral corticosteroid (e.g., prednisone) at an equivalent dose at start of tapering or earlier, once sustained clinical improvement is observed. Lower bioavailability of oral corticosteroids should be taken into account when switching to the equivalent dose of PO corticosteroids.

CONFIDENTIAL

This document is confidential. Do not disclose or use except as authorized.

[figure not shown]
Endocrinopathy Management Algorithm

CONFIDENTIAL

This document is confidential. Do not disclose or use except as authorized.

Neurological Toxicity Management Algorithm

[figure not shown]

Patients on IV steroids may be switched to oral corticosteroid (e.g., prednisone) at an equivalent dose at start of tapering or earlier, once sustained clinical improvement is observed. Lower bioavailability of oral corticosteroids should be taken into account when switching to the equivalent dose of PO corticosteroids.

CONFIDENTIAL

This document is confidential. Do not disclose or use except as authorized.

Skin Toxicity Management Algorithm

Patients on IV steroids may be switched to oral corticosteroid (e.g., prednisone) at an equivalent dose at start of tapering or earlier, once sustained clinical improvement is observed. Lower bioavailability of oral corticosteroids should be taken into account when switching to the equivalent dose of PO corticosteroids.

CONFIDENTIAL

This document is confidential. Do not disclose or use except as authorized.

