5.2.2 Other Cycles

To proceed with subsequent cycles, subjects must not have:

- grade 2 or higher acute GVHD (see **Appendix C** for GVHD grading) requiring systemic immunosuppression
- extensive (or severe) chronic GVHD requiring systemic immunosuppression
- ongoing non-hematologic toxicity of grade 2 or higher unrelated to underlying malignancy or GVHD

Subjects will be allowed to proceed to subsequent cycles if they have ongoing:

- immune-related adverse events not defined as GVHD (e.g. diarrhea, pruritus, endocrinopathy, and rash) that have responded to corticosteroids and improve to grade 1 or less

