6.1.3 Ipilimumab Dose Modifications/delays

Intra-patient dose modifications of Ipilimumab are not allowed in this study as lower doses have not been found to be less likely to lead to resolution of immune-related AEs that were seen at higher doses.

Decisions to delay an Ipilimumab dose will be made based on specified safety criteria. Treatment with Ipilimumab will be delayed or discontinued if the subject experiences at least one adverse event, specified below, considered by the

CONFIDENTIAL

This document is confidential. Do not disclose or use except as authorized.

investigator to meet the criteria as outlined. The investigator should contact the Protocol Chair for any adverse event that will prompt a delayed dose or discontinuation of Ipilimumab. The following criteria will be used to determine dose delays, restarting doses, or discontinuing Ipilimumab:

It is necessary to delay study drug dosing for the following related adverse event(s):

- Any \geq Grade 2 non-skin related adverse event (including irAEs), except for asymptomatic laboratory abnormalities
- Any \geq Grade 3 laboratory abnormality
- Any adverse event, laboratory abnormality or intercurrent illness that, in the judgment of the investigator, presents a substantial clinical risk to the subject with continued dosing
- Any \geq Grade 3 skin related adverse event regardless of causality

Restart Ipilimumab dosing if/when the adverse event(s) resolve(s) to \leq Grade 1 severity or return to baseline within 3 weeks of initiating the dose delay (no more than 6 weeks since the most recent prior dose administration).

The maximum amount of time that induction Ipilimumab can be delayed due to adverse events before patients must be taken off treatment is 3 weeks, (i.e. 6 weeks between doses, respectively). Patients on maintenance Ipilimumab dosing must be taken off treatment if dosing is delayed for more than 4 weeks due to toxicity.

In the event of a dose delay:

- Certain study assessments, including bone marrow biopsy, T-cell chimerism, tumor measurement (CT or PET/CT), and/or correlative study samples associated with day 1 of the delayed cycle may be assessed on the original planned cycle day 1 (first day of dose delay) only (do not need to be re-assessed on actual cycle day 1, the day of cells and Ipilimumab infusion)

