mg/kg/day of prednisone or equivalent. Upon improvement to grade 1 or less, initiate corticosteroid taper and continue to taper over at least one month. In clinical trials, rapid corticosteroid tapering has resulted in recurrence or worsening symptoms of enterocolitis in some patients.

Immune-mediated Hepatitis and Pancreatitis

Hepatic immune-related AEs were mostly clinically silent and manifested as transaminase or bilirubin laboratory abnormalities. Fatal hepatic failure has been reported in clinical trials of Ipilimumab. Serum transaminase and bilirubin and lipase levels must be evaluated before each dose of Ipilimumab as early laboratory changes may be indicative of emerging immune-related hepatitis/ pancreatitis and elevations in liver function tests (LFTs) may develop in the absence of clinical symptoms. Increase in LFT or total bilirubin should be evaluated to exclude other causes of hepatic injury, including infections, disease progression, or other medications, and monitored until resolution. Liver biopsies from patients who had immune-related hepatotoxicity showed evidence of acute inflammation (neutrophils, lymphocytes, and macrophages), and biopsy should be considered in patients with grade 2 and higher hepatotoxicity (to distinguish GVHD vs. immune-related hepatotoxicity).

Monitor liver function tests (hepatic transaminase and bilirubin levels, lipase) and assess patients for signs and symptoms of hepatotoxicity/ pancreatitis before each dose of Ipilimumab. Withhold Ipilimumab in patients with grade 2 hepatotoxicity and consider liver biopsy (to distinguish GVHD vs. immune-related hepatotoxicity).

Permanently discontinue Ipilimumab in patients with grade 3–5 hepatotoxicity/ pancreatitis, consider liver biopsy (to distinguish GVHD vs. immune-related hepatotoxicity), and administer systemic corticosteroids at a dose of 1 to 2 mg/kg/day of prednisone or equivalent. When liver function tests show sustained improvement or return to baseline, initiate corticosteroid tapering and continue to taper over 1 month.

Immune-mediated Dermatitis

Skin immune-related AEs presented mostly frequently as a rash and/or pruritus. Some subjects reported vitiligo associated with Ipilimumab administration. Fatal toxic epidermal necrolysis has been reported in clinical trials of Ipilimumab.

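### For some hepatic events above grade 2, Section 6.1.13 ends ipilimumab permanently while Appendix G and Section 6.1.3 allow a hold and later resumption, and no text says which prevails

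*Combined protocol and SAP*

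**What the plan says.** Liver events are covered in three places.

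- Section 6.1.13, on immune-mediated hepatitis and pancreatitis, has two steps. At grade 2: "Withhold Ipilimumab in patients with grade 2 hepatotoxicity and consider liver biopsy". Above that: "Permanently discontinue Ipilimumab in patients with grade 3–5 hepatotoxicity/ pancreatitis". The second step makes no exception by enzyme or bilirubin level.
- Appendix G, in the footnote to the hepatotoxicity algorithm, says: "Ipilimumab may be held/delayed rather than discontinued if AST/ALT" is at most 8 × ULN and total bilirubin is at most 5 × ULN. Resumption then has two conditions: "Resume ipilimumab when AST/ALT/Tbili return to grade 2 and meet protocol specific retreatment criteria".
- Section 6.1.3 makes a delay necessary for a related laboratory abnormality of grade 3 or higher. Dosing restarts when the event has resolved to at most "Grade 1 severity or return to baseline within 3 weeks of initiating the dose delay".

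Skin events are also worded in more than one way. Section 5.2.2 bars a further cycle while there is "ongoing non-hematologic toxicity of grade 2 or higher unrelated to underlying malignancy or GVHD", with no exception for skin. Section 6.1.3 restricts its grade 2 delay trigger to events outside the skin and makes a skin delay necessary only from "Grade 3 skin related adverse event regardless of causality".

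**The concern.** Permanent discontinuation and a hold with later resumption are different instructions for the same patient. If both apply to one event, whether that patient receives more ipilimumab depends on which page the treating physician opens.

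This matters more here than in most trials. Safety is the primary objective. Section 6.1.13 notes that fatal hepatic failure has been reported with ipilimumab, and Section 2.2.2 lists chronic GVHD of the liver among the DLTs of the earlier ipilimumab trial after transplant. Under Section 5.4, a non-neurologic immune-related event of grade 3 or higher that responds to corticosteroids and improves to grade 1 or less within 3 weeks is not a DLT. For such a patient the DLT rule records nothing, and only the continuation rules decide on re-exposure. Section 13.4 also records that delayed SAEs contributed to the return to dose level 0, so exposure after the DLT window is relevant to this trial's conclusions.

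**Working it through.** The plan gives no figure to reproduce, and no power or error-rate formula applies. The check sets the passages side by side and follows one case through them.

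**Step 1: the liver passages.**

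| Place | Trigger | Action | Return to dosing |
|---|---|---|---|
| 6.1.13 | Hepatotoxicity grade 3–5 | Permanent discontinuation | None |
| Appendix G footnote | AST/ALT ≤ 8 × ULN and bilirubin ≤ 5 × ULN | Hold or delay allowed in place of discontinuation | Grade 2, plus protocol retreatment criteria |
| 6.1.3 | Related laboratory abnormality grade ≥ 3 | Delay | Grade ≤ 1 or baseline, within 3 weeks |

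**Step 2: do the triggers overlap?** The footnote speaks of tests returning to grade 2, and of holding as an alternative to discontinuing. Both imply that the event was above grade 2, which is the range that 6.1.13 assigns to permanent discontinuation. The overlap is therefore hepatic events above grade 2 and within both ceilings. This is an inference from the footnote: the algorithm figure is not shown, and the protocol does not reproduce the CTCAE liver cut-offs.

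**Step 3: one case.** Take a related grade 3 hepatic laboratory event within the ceilings that falls to grade 1 within 3 weeks, in a patient who is not on systemic corticosteroids when the next dose is considered. Under 6.1.13 there is no further ipilimumab. Under Appendix G the drug may be held and resumed. Under 6.1.3 it is delayed and restarted. Section 6.1.4, which lists the criteria for permanent discontinuation, does not name hepatotoxicity; it leaves events outside its list to the investigator's judgment.

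**Step 4: can resumption actually occur?** Section 6.1.4 bars a restart during systemic corticosteroids, except stable hormone replacement. Section 6.1.13 tapers steroids over 1 month after a severe liver event. That is longer than the 3-week limit on induction delay, so a steroid-treated event often closes the induction route, unless the study chair grants the exception in 6.1.3. It need not close the maintenance route. The scheduling table puts Cycle 4 Day 1 at day 64, Cycle 5 Day 1 at day 169 and Cycle 6 Day 1 at day 253. The gaps are 169 − 64 = 105 days and 253 − 169 = 84 days. An event early in such a gap can resolve and be tapered before the next dose is due, with no delay at all. The conflict therefore has practical content.

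**Step 5: the skin passages.** Take an ongoing grade 2 rash that is due to neither GVHD nor the malignancy. Section 5.2.2 bars the next cycle. Section 6.1.3 does not make a delay necessary, but does not direct dosing either. The dermatitis text in 6.1.13 withholds for moderate to severe signs, having placed grade 2 localized rash under mild to moderate. The thresholds differ, but all can be met by applying the strictest.

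**The case against.** The best defence has four parts.

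1. *The texts are guidance.* Section 6.1.9 describes 6.1.13 and Appendix G together as recommendations, to be used as clinically appropriate, and Section 5.6 points to 6.1.3 for temporary or permanent stopping. This lowers the force of the conflict without settling it. Both texts have the same status, no precedence is set between them, and 6.1.13 says that its approach will be followed in this study.
2. *The resumption clause defers to the protocol.* This is correct. A reader might infer that Appendix G lets dosing resume at grade 2 alone. It does not: the protocol's retreatment criteria must also be met, and these can be read as the restart rule in 6.1.3 and the conditions in 5.2.2. On the restart threshold, Appendix G and 6.1.3 are compatible, so it would be wrong to count three competing liver rules. The deferral cannot remove the difference between never restarting and possibly restarting.
3. *Section 6.1.3 is general and 6.1.13 is organ-specific,* so the specific text could be taken to govern. That may dispose of 6.1.3 taken alone. It does not help with Appendix G, which is equally specific to the liver.
4. *The DLT definition does not depend on these rules.* Section 5.4 classifies events by grade, persistence and relatedness. That stands: the MTD classification is not directly affected.

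A reader might also infer a direct contradiction on skin. The documents do not support it. Section 6.1.3 lists when delay is necessary and allows delay for any other event on the investigator's judgment, so both sections can be obeyed at once. The Section 5.2.2 condition also leaves out GVHD-related toxicity.

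**Conclusion.** The liver conflict is real in the current text. For hepatic events above grade 2 with AST/ALT at most 8 × ULN and bilirubin at most 5 × ULN, one passage ends ipilimumab permanently, and two others allow delay and a later return. Nothing ranks them.

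Two wider readings should be resisted. One is that all severe hepatotoxicity is affected: the Appendix G hold stops at its ceilings, and above them it does not conflict with 6.1.13. The other is that the effect can be sized by counting the doses left after an event. Such a count gives remaining visits, not the effect of the inconsistency. It also changes according to whether the dose due on the day of detection had been given, and it has no firm upper limit, because Section 5.3.1 allows dosing beyond Cycle 8 with approval.

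The size is therefore qualitative: an ambiguity about re-exposure in a defined subset of liver events, whose frequency the documents do not give. For scale only, phase 1b has 10 patients, so one patient handled under a different section is 1/10 = 10% of that cohort. The conclusion rests on the inference that the footnote concerns events above grade 2, and on the footnote without its figure. The skin wording is a secondary point of harmonisation.

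**What to change.** Reconcile Section 6.1.13, Section 6.1.3 and the Appendix G footnote into one hepatic rule, stated once, with the other two places referring to it. The rule should say whether any event above grade 2 may be held instead of ending treatment, whether enzyme and bilirubin ceilings apply, and which criteria count as the protocol's retreatment criteria. Each of these is the sponsor's clinical choice, and this review takes no position on them. In the same edit, align the skin wording of Sections 5.2.2 and 6.1.3 and the dermatitis text of 6.1.13, or state that all conditions must be met together.

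In the analysis, list hepatic discontinuations, holds and resumptions by patient under the reconciled rule, so that exposure at the recommended dose can be interpreted. The cost is a wording amendment and one descriptive listing; sample size, visits and endpoints do not change.
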